12.9.2 Secondary Efficacy Analyses

12.9.2.1 Change in WHO Severity Scores

12.9.2.1.1 Shift Summary

Shift in WHO severity scores from baseline (scores 4-6) to each post-baseline visit (Days 2, 3, 7, 14, 28, 60 and 90) will be presented by treatment groups. Subjects whose values are missing or assessment is not done will be presented as 'Missing / Not Done'. Percentages will be based on corresponding population.

In DDP: Tables 14.2.2.1 and 14.2.2.2

12.9.2.1.2 Box Plot

Box plot will be plotted to visualize the trend in average WHO Severity scores at baseline and post-baseline visits (Days 2, 3, 7, 14, 28, 60 and 90). X axis will represent visit and Y axis will represent WHO severity scores. Each treatment group will be plotted in a separate page. Number of subjects at each visit will be annotated below the X-axis.

In DDP: Figures 14.2.2.3 and 14.2.2.4

12.9.2.1.3 MMRM

WHO Severity score change from baseline to each visit will also be analyzed using a mixed model for repeated measures under missing at random framework using WHO scores collected at scheduled visits. Change from baseline to each visit will be specified as the dependent variable. Treatment group, visit, baseline WHO Score and an interaction effect between treatment-by-visit and baseline WHO score-by-visit will be specified as independent variables. Least square estimates of the mean change from baseline and confidence intervals of this estimate will be created for each treatment group by the model. Treatment group will be compared with the Placebo group in a pairwise fashion at each visit.

Further, the difference in the dependent variable between the treatment groups will be estimated for each of these comparisons, as well as 95% confidence intervals for these estimates and p-values

testing the null hypothesis that the difference between the treatment groups is zero. All these hypothesis tests will be made using the same mixed model for repeated measures. The approach allows for the repeated measures within subjects to be taken into account. An unstructured covariance will be assumed to allow the variances and covariances to differ between visits and treatments.

Reference SAS Program:

```
proc mixed data = XXX;
  class trta subjectid visit;
  model chg = trta visit bsl_who trta*visit bsl_who*visit;
  repeated visit / subject=subjectid type=un;
  lsmeans trta*visit / diff cl pdiff;
  lsmeans trta / diff cl pdiff;
run;
```

Reference: Tables 14.2.2.5 and 14.2.2.6

12.9.2.1.4 Listing

WHO Severity scores for all visits will be listed by subject and grouped by treatment groups.

In DDP: Listing 16.2.6.1

12.9.2.2 Time to Death (Days)

12.9.2.2.1 Log-Rank Test

Time-to-event statistics including number of subjects with event (see section 11.18), censored, mean, standard error, median time along with 95% CI, 25th and 75th quartiles, minimum and maximum will be reported in a summary table. Log Rank test will be performed to compare the survival probability curves between treatment groups and corresponding unadjusted p-values will be included.

Percentage of subjects alive at Day 28 and Day 90 will be estimated using Kaplan-Meier method. 95% CI for the point estimate will also be presented.

Reference SAS Program:

```
proc lifetest data =  plots=survival;
  time <duration>*<censor> (1);
  strata <treatment>/ test=LOGRANK;
run;
```

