### 5.2.2. Secondary Endpoints

- Safety and tolerability
  - Incidence, causality, and severity of AEs (graded according to the National Cancer Institute [NCI] Common Terminology Criteria for Adverse Events [CTCAE] version 5.0) in rhu-pGSN vs placebo groups
  - Frequencies of new or worsening clinically significant laboratory abnormalities in rhu-pGSN vs placebo groups
  - Mortality rate irrespective of cause at Days 28 and 90
- Efficacy
  - Daily change in 9-point WHO severity score through at least Day 14 (including after discharge, where feasible)
  - All-cause mortality at Days 28 and 90; time to death (Kaplan-Meier survival analysis)
  - Proportion of subjects alive on Days 7, 14, 28, 60, and 90 without:
    - Ongoing use of vasopressors
    - Ongoing intubation/mechanical ventilation
    - Ongoing residence in an ICU
    - New ongoing need for dialysis/renal replacement therapy (RRT)
  - Proportion of subjects discharged to home or immediate prior residence by Day 28
  - Days on the ventilator
  - Length of stay (LOS) in hospital and in ICU (days)
  - Re-admission to an acute-care hospital up to Day 90
- PK
  - PK for rhu-pGSN including maximum concentration ( $C_{max}$ ), time to maximum concentration ( $T_{max}$ ), terminal half-life ( $T_{1/2}$ ), area under the curve from time zero to 8 hours ( $AUC_{0-8}$ ), area under the curve from time 0 to infinity ( $AUC_{inf}$ ) for Dose #1 within 15 minutes predose, and at 1 ( $\pm 15$  min), 2 ( $\pm 15$  min), 6 ( $\pm 30$  min), and 12 ( $\pm 30$  min) hours after end of administration (but prior to Dose #2); for Dose #3 within 15 minutes predose, and at 1 ( $\pm 15$  min), 2 ( $\pm 15$  min), 6 ( $\pm 30$  min), 12 ( $\pm 30$  min) and 24 ( $\pm 30$  min) hours after the end of administration (participants refusing these blood samplings can enter and remain in the trial).
- Immunogenicity
  - Presence of anti-pGSN antibodies on Days 1 (predose), 28, and 90

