## **6.5. Study Duration**

Subjects will be treated with 3 doses over 36 hours: after the initial dose is administered (Dose #1), then next dose (Dose #2) is administered 12 hours later, and the last dose is administered 24 hours later (Dose #3 administered 36 hours after Dose #1).

Subject screening will occur for Part 1 within 24 hours of determination of WHO severity score of 4 to 6, whether the severity score is attained on admission or during current ongoing hospitalization, or for Part 2, within 24 hours of intubation without ECMO with a WHO severity score of 6 or 7. Eligible subjects will be randomized within 12 hours of informed consent (Part 1) or 24 hours of intubation (Part 2), and dosed within 12 hours of randomization (both parts).

Subjects are followed for safety and efficacy through Day 90.

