8.1 General Conventions

All analyses will be done using SAS (version 9.4, SAS Institute Inc., Cary, NC, USA).

Efficacy and Safety endpoints will be analyzed in a descriptive manner. Continuous data will be reported using the following descriptive statistics:

1. Number of observations (n)
2. Mean and Standard deviation (SD)
3. Interquartile Range (IQR)
4. Minimum (min) and Maximum (max)
5. Median

In addition:

6. Geometric mean & Standard deviation
7. Coefficient of variation (CV%)
8. Geometric CV%

will be reported for plasma concentration data and PK parameters. Categorical data will be presented using frequency (n = number of subjects; m = number of events) and percentage (%).

Listings will be provided for all data recorded in eCRF to study subject profiles. All listings will be sorted by treatment, subject ID, and date (if applicable). Unscheduled visit data will only be listed and not included in summaries.

All p-values will be displayed to four decimal places, with p-values less than 0.0001 presented as '<0.0001' and p-values greater than 0.9999 presented as '>0.9999'. Minimum and maximum values will be reported in the units of collection with 3 decimals being maximum value; the mean will be presented with 1 decimal place more and the standard deviation 2 decimal places more than the units of collection. Percentages for categorical summaries will be represented to 1 decimal place.

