11.18 Time to Death

Time to Death will be calculated as follows:

- Time to Death = (Date of Death – Date of First IMP) + 1

Subjects without death in the trial will be censored at either the date of withdrawal or the date of last visit, whichever occurs earlier.

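### SAP 12.9.2.2.1 reports a mean time to death per arm with no common time limit, so the two means are not comparable

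*SAP*

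**What the plan says.** Protocol 5.2.2 names the endpoint as "All-cause mortality at Days 28 and 90; time to death (Kaplan-Meier survival analysis"; it does not ask for a mean. SAP 12.9.2.2.1 adds one. Its summary table is to show the numbers with an event and "censored, mean, standard error, median time along with 95% CI, 25th and 75th quartiles, minimum and maximum will be reported".

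The reference program is a plain PROC LIFETEST call with "strata <treatment>/ test=LOGRANK", so each arm has its own curve and its own mean. The call has no TIMELIM or RMST option, and no text elsewhere limits the mean to a stated day. The software is SAS 9.4 (SAP 8.1).

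On follow-up, Protocol 6.5 says "Subjects are followed for safety and efficacy through Day 90", and SAP 11.18 says "Subjects without death in the trial will be censored at either the date of withdrawal or the date of last visit, whichever occurs earlier".

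The same part of the SAP also plans a log-rank test, Kaplan-Meier percentages alive at Days 28 and 90 with 95% CIs, a Cox hazard ratio in the same table (12.9.2.2.2), and curves with numbers at risk (12.9.2.2.3).

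**The concern.** A mean survival time cannot be estimated when the curve does not reach zero. It needs a time limit, and the limit must be the same in both arms if the means are to be read side by side. Here survivors are censored, so unless nearly everyone dies the longest times in each arm will be censored.

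With no limit given, the program supplies one. By default LIFETEST integrates each curve only to that arm's last death. Fewer deaths tend to put the last death earlier, which shortens the mean. The effect of rhu-pGSN on survival is a secondary objective, so a favourable hazard ratio could sit in the same table as a shorter mean survival for the active arm.

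**Working it through.** **Inputs**

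- Arm size: 30 per arm in Part 1 (Protocol 7.1).
- Last visit: Day 90 ± 4 (Protocol Table 5). Survivors are censored at withdrawal or last visit (SAP 11.18).
- Stopping rule: each arm's last death. This is an assumption about the named procedure and is not in the SAP.
- Death rates and timing: assumptions, because neither document gives a Day 90 mortality for this trial. The 20% and 5% in SAP 4.2 concern a Day 14 composite. Their power statement reproduces (27 per arm, one-sided 0.2, gives 80.1%), but it only hints at the size of the death rates. The plan has no time-to-death figure to reproduce.

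**Formula**

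Mean to limit L = Σ S(t[i−1]) × (t[i] − t[i−1]), summed up to L. The default takes L as the arm's own last death. The comparison takes L = 90 in both arms.

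**Illustration (30 per arm, all survivors followed to Day 90)**

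- Arm A, one death on Day 10. Default: 10 × 1 = 10.0 days. To Day 90: 10 + 80 × 29/30 = 87.3 days.
- Arm B, six deaths on Days 8, 12, 15, 20, 28 and 45. Default: 8 + 4 × 29/30 + 3 × 28/30 + 5 × 27/30 + 8 × 26/30 + 17 × 25/30 = 40.3 days. To Day 90: 40.3 + 45 × 24/30 = 76.3 days.

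The default puts the arm with one death 30 days below the arm with six. The common limit puts it 11 days above. One death against six is a near-extreme split, so this shows the mechanism and not its typical size. In Arm A no area remains after the only death, so the usual variance sum is zero and a standard error carries no information.

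**How often the order reverses**

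Simulated trials, 30 per arm, 4,000 per scenario, 5% dropout. Four timing patterns were used: uniform, constant hazard, early (exponential, mean 20 days) and mid (gamma, mean 21 days). Counted among trials with unequal deaths and at least one death in each arm:

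| Assumed Day 90 mortality | Arm with fewer deaths shows the shorter mean |
|---|---|
| 10% vs 5% | 66-70% |
| 15% vs 5% | 67-71% |
| 20% vs 5% | 66-72% |
| 20% vs 10% | 60-66% |
| 20% vs 15% | 55-61% |
| 30% vs 15% | 49-61% |
| 40% vs 20% | 37-55% |
| 50% vs 30% | 25-48% |

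With other timing patterns added (for example, deaths uniform to Day 28 or to Day 60), 5-10% against 10-20% gives 59-73%. With a common Day 90 limit the figure is 0-10%. At 20% vs 5% it is 0.1-4%.

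**Arms with no deaths**

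The chance of no deaths in 30 at 5% mortality is 0.95^30 = 0.215. At 10% it is 0.9^30 = 0.042, and at 20% it is 0.8^30 = 0.001. The chance that at least one arm has none is 1 − 0.785 × 0.958 = 0.248 for 5% vs 10%, and 1 − 0.785 × 0.999 = 0.216 for 5% vs 20%. The simulations gave 21-26%. Such an arm has no estimable mean. Counting every trial, the rhu-pGSN mean is shorter in 44-47% (5% vs 10%), 51-56% (5% vs 20%) and 55-60% (10% vs 20%).

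**Neighbouring statistics**

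The median needs about half the arm to die. The first quartile needs 8 deaths of 30 (22/30 = 0.733; 23/30 = 0.767 is not enough). At 20% mortality, P(at least 8 of 30) = 0.239. The mean may therefore be the only location figure printed for an arm.

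**The case against.** The strongest reply has three parts.

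First, the stopping rule is software behaviour, and the SAP's program is offered only as a reference. This stands as a limit. What the SAP itself shows is a mean with no horizon. If the mean were instead run to each arm's longest follow-up, the spans would usually differ by only a few days, given the Day 90 ± 4 window, and the problem would be slight. The Data Display Plan, which holds the table layout, is a separate document and might add a footnote. But the SAP should not leave the horizon to a program default.

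Second, a reader might infer that the table will usually rank the arms the wrong way, so that a survival benefit would normally look like harm. The documents do not support that. They give no Day 90 mortality for this population. The percentages above one half depend on a death in each arm and on mortality of about 20% or less. Counting all trials, the figure is near one half. At higher mortality the reversal is often not the usual result, and the ICU study in Protocol 4.4.2 saw 7 deaths in 21 treated patients (33%).

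Third, the mean is not a named analysis. SAP 16.1 lists the log-rank test, Cox model and Kaplan-Meier curve for time to death. No test or between-arm difference of means is planned, and the event counts and hazard ratio stand in the same table. This stands too, and it is why the point is minor.

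**Conclusion.** The point holds as a reporting defect. As written, the two means cover different, data-driven spans and cannot be compared. With the LIFETEST default, assumed mortality of 5-10% against 10-20% and a death in each arm, the arm with fewer deaths shows the shorter mean in about 59-73% of 30-per-arm trials. A common limit removes most of this. Closer rates weaken it (55-61% at 20% vs 15%). From about 30% mortality, the result depends on when the deaths occur.

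The effect is confined to one descriptive line. The primary endpoint, log-rank test, hazard ratio, Day 28 and Day 90 percentages and curves are unaffected. The reversal rates rest on assumed death rates and timing and on a software default; the missing time limit does not.

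**What to change.** Delete the unrestricted mean and standard error from the table in SAP 12.9.2.2.1. Nothing planned depends on them, and the protocol's own list of time-to-event summaries for Part 2 (Protocol 11.1) has no mean.

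If a mean is wanted, replace it with a restricted mean to one pre-stated time used in both arms. Day 28 is one natural choice. A later limit should be no greater than the shorter of the two arms' longest follow-up, because the last visit is Day 90 ± 4 and survivors may be censored before Day 90. A between-arm contrast of restricted means is optional.

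In either case, show the median and quartiles as not reached where that applies. The cost is one sentence in the SAP and, if a restricted mean is kept, one program option. No new data are needed.

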12.9.2.2.2 Cox Proportional Model

Cox regression will be performed with WHO Severity score at baseline as continuous covariate in the model to compare hazard between treatment and placebo and to estimate hazard ratio. Hazard Ratio along with 95% CI will be reported in the same table mentioned in section 12.9.2.2.1.

Reference SAS Program:

```
proc phreg data=<data> ;
  class treatment;
  model time*status (01) =treatment bsl_who/r1;
```

```
hazardratio 'Treatment vs Placebo' treatment;
run;
```

In DDP: Tables 14.2.3.1 and 14.2.3.2

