11.2 Treatment groups

All analyses will be summarized by treatment group. The following treatment groups will be defined in the analysis datasets.

- rhu-pGSN
- Placebo

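### The SAP's reference Cox program names no reference arm; with the SAP's own group names, SAS defaults give placebo versus rhu-pGSN under a 'Treatment vs Placebo' title

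*SAP*

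**What the plan says.** SAP 8.1 fixes SAS 9.4 as the software. SAP 11.2 introduces the two arms with "The following treatment groups will be defined in the analysis datasets" and lists rhu-pGSN, then Placebo. It gives no variable type, stored code, format or level order.

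SAP 11.18 defines the time variable as "Time to Death = (Date of Death – Date of First IMP) + 1", so the event is death and a hazard ratio below 1 for rhu-pGSN against placebo means benefit.

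SAP 12.9.2.2.2 says of the model that "Cox regression will be performed with WHO Severity score at baseline as continuous covariate in the model", and gives its purpose as "to compare hazard between treatment and placebo and to estimate hazard ratio". The reference program contains "class treatment" with no further option, and then "hazardratio 'Treatment vs Placebo' treatment", again with no option. On reporting: "Hazard Ratio along with 95% CI will be reported in the same table mentioned in section 12.9.2.2.1".

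No section of the SAP says which arm is the reference, or that a hazard ratio below 1 favours rhu-pGSN.

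**The concern.** The text and the title both point to rhu-pGSN against placebo, but nothing in the program produces that direction. The words in quotation marks in the hazard ratio statement are a free-text title. The direction comes from the level order and the reference level, and both are left to software defaults. With the group names in SAP 11.2, those defaults lead to the opposite contrast.

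The hazard ratio is the only between-arm effect size in SAP 12.9.2.2; the log-rank test gives a p-value, and the other summaries are per arm. Reversal changes neither the p-value nor whether the interval includes 1, so the test result would not reveal it. Direction matters both ways. Protocol 4.4.2 reports an earlier ICU study with 7 deaths among 21 rhu-pGSN patients and none on placebo, which it attributes most probably to baseline imbalance. A mortality hazard ratio for this product should leave no doubt about which arm is in the numerator.

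**Working it through.** The plan states no hazard ratio, assumed hazard ratio or number of deaths, so there is no figure of its own to reproduce. The check traces the program.

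**Inputs from the SAP**
- Software: SAS 9.4 (8.1).
- Arm names: rhu-pGSN and Placebo (11.2).
- Class statement: no `ref=`, `order=` or `param=` (12.9.2.2.2).
- Hazard ratio statement: a title only, no `diff=` (12.9.2.2.2).
- Intended contrast: treatment against placebo (12.9.2.2.2).

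**Assumed software behaviour (standard PROC PHREG defaults, not stated in the documents)**
- Class levels are sorted by formatted value, or by internal value for an unformatted numeric variable.
- The last level is the reference.
- With two levels and no `diff=` option, the hazard ratio statement gives one comparison, first level versus last.

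**Step 1: level order.** The names sort as Placebo, rhu-pGSN, whether or not case is considered. The reference is therefore rhu-pGSN.

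**Step 2: contrast produced.** HR produced = hazard(placebo) / hazard(rhu-pGSN) = 1 / HR intended. The new lower limit is 1 / old upper limit, and the new upper limit is 1 / old lower limit. The log hazard ratio only changes sign, so the p-value is the same.

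**Step 3: size, for assumed intended values.**

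| Intended (rhu-pGSN vs placebo) | Produced under the title |
|---|---|
| 0.25 | 1/0.25 = 4.00 |
| 0.50 | 1/0.50 = 2.00 |
| 0.75 | 1/0.75 = 1.33 |
| 0.50 (95% CI 0.20 to 1.25) | 2.00 (1/1.25 = 0.80 to 1/0.20 = 5.00) |

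**Step 4: one simulated trial.** With 30 per arm, an assumed true hazard ratio of 0.5 and the baseline WHO score as a continuous covariate, one simulated dataset had 13 deaths. The fit gave 0.38 (0.12 to 1.25) with Placebo as reference and 2.63 (0.80 to 8.65) with rhu-pGSN as reference. This was run in Python with each reference set by hand. It shows the size of the reversal at this trial's scale; it does not test the SAS defaults.

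**Step 5: dependence on coding, under the same defaults.**

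| Content of the arm variable | Last level (reference) | Contrast produced |
|---|---|---|
| Character values Placebo, rhu-pGSN | rhu-pGSN | reversed |
| Numeric code formatted with those names | rhu-pGSN | reversed |
| Unformatted numeric code, placebo first | rhu-pGSN | reversed |
| Unformatted numeric code, placebo last | Placebo | as intended |

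A sort sequence that places lower-case letters before upper-case ones (EBCDIC) would also give the intended direction with the character names.

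**The case against.** The strongest reply is that this is a template. It is headed as a reference program, uses a placeholder for the dataset and must be completed before use. SAP 11.2 gives group names, not stored values, and the arm variable is not even named consistently: it is `trta` in the mixed-model program and `treatment` here. SAP 11.2 lists rhu-pGSN first, so an unformatted 1/2 code in that order would put placebo last and give the intended direction. The mechanism also rests on software defaults that the documents do not describe. All of this stands, and it makes the finding conditional. It does not remove the finding: the program is the only place where the SAP specifies how the contrast is formed, and the only arm labels the SAP supplies lead to the reversed one.

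A second reply is that a reversal would be noticed. The SAS output row would itself read Placebo vs rhu-pGSN beneath the title. The same table carries event counts and medians, Kaplan-Meier percentages alive at Days 28 and 90 are estimated (SAP 12.9.2.2.1), curves are drawn by arm (12.9.2.2.3), and deaths are tabulated by arm (12.10.2). This also stands. A reader might infer that the trial would report a survival benefit as harm. The documents do not support that: it would require the arm coding to be as assumed, the row label to be passed over, and the adjacent per-arm results to be ignored.

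A third reply is that the prose already fixes the intended direction and should govern. It does convey the intent, but it gives neither a reference level nor an interpretation of values below 1, and the code does not carry the intent out.

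**Conclusion.** The point holds in conditional form. If the class variable contains, or is formatted with, the names in SAP 11.2, and SAS defaults apply, the number produced under the title is the reciprocal of the intended hazard ratio. Its confidence limits are inverted and exchanged, and its p-value is unchanged. If the variable is an unformatted numeric code with placebo last, the output is as intended. The SAP does not say which applies.

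Severity is low. Time to death is a secondary endpoint. Protocol 11.1 describes the Cox model as a possible supplemental analysis, although SAP 16.1 lists it alongside the log-rank test and Kaplan-Meier curve for mortality. The primary endpoint, the log-rank test and the survival estimates are unaffected. It is still more than a missing detail, because the stated code, group names and title do not agree with one another under the defaults.

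**What to change.** In SAP 12.9.2.2.2:

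- Replace the class statement with `class treatment (ref='Placebo');`, with the value in `ref=` matched to the actual stored or formatted placebo level.
- Replace the hazard ratio statement with `hazardratio 'rhu-pGSN vs Placebo' treatment / diff=ref;`, so that the comparison is made against the named reference and the title matches it.
- Add one sentence: the hazard ratio is rhu-pGSN versus placebo, and a value below 1 favours rhu-pGSN.

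The cost is two lines of code and one sentence. No data, population, model or p-value changes, and the direction no longer depends on how the arm variable is coded.
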